2.3.3 SAFETY OUTCOMES

Adverse events listed by MedDRA terms will be tabulated by allocated treatment. Serious adverse events will be tabulated by allocated treatment. Suspected unexpected serious adverse reaction listed by MedDRA terms will be tabulated by allocated treatment.

2.3.4 SENSITIVITY ANALYSES

The sensitivity analyses planned were chosen in line with the view that sensitivity analyses should address exactly the same question as the main analyses but be valid under different (potentially verifiable) assumptions, and that if the results are qualitatively different to those in the main analysis, there would be genuine doubt as to which are the correct results. If this does occur, both the main analyses and the results of the sensitivity analyses will be reported in a transparent manner.

Correlation structure

We will explore the robustness of conclusions to different assumptions about the correlation structure of residual errors between the primary outcome measures from the same participant within the same week.

Fixed treatment effect

We will compare the main analyses with random treatment effects to models with a fixed treatment effect only.

Period and carry-over effects

We will add fixed period effects to the primary and secondary outcome models. Because participants will start their individual N-of-1 trials at different times of the year, there is no reason to expect there to be a period effect. We will not explore carry-over effects; the trial was designed to avoid such effects.

Missing data

The mixed model described above is valid under outcome data being missing at random given the observed outcome data. We will use multiple imputation to perform an analysis valid under missing at random given both the observed outcome data and the measured baseline characteristics. We will then consider a number of simple scenario analyses to assess the robustness of our findings to outcome data being missing not at random.

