2.9.3 ADMINISTRATION OF TRIAL MEDICATION

Patients will receive their allocated trial medications through the post and they will be asked to take the study medication daily through the six two-month treatment periods. Ideally there should be no break between treatment periods. However, if for any reason there is a break, patients can simply restart taking the trial medication as soon as possible.

Patients will be asked to take one capsule orally once daily at a time of day convenient to them. Capsules should be swallowed whole. Patients will be given written instructions on how to take the study medication. At the start of each two-month treatment period, patients will be asked to inform the trial team about their first date of study medication use using the trial's mobile application (app), email, text message, Freephone telephone service or a pre-paid postage reply slip - whichever is easier to ensure data collection occurs on the correct days. A Freephone telephone number will be provided for patients to call if they have any questions. Adherence to the study medication will be collected on the same days as other data as part of the outcome data collection.

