Appendix 4: StatinWISE Patient questionnaire

INSTRUCTIONS

This questionnaire is to be filled out once every two months (on day 56). We will remind you one day before it is due. Please answer all questions. If you need any help to complete the form. Please call our Freephone number [name] or email the study team: [contact].

PART 1: ADHERENCE TO MEDICATION

Step 1 (all participants):

Q1. How would you best describe your use of study medication in the past two months? (Please choose one of the following options)

- I didn't take my study medication at all
- I took my study medication on some days
- I took my study medication on most days, but missed an occasional dose
- I took my study medications every day

Step 2 (appears if the participant chooses "I didn't take my study medication at all", or "I took my study medication on some days"):

Q2. What was the reason that you didn't take your study medication every day in the past two months? (please tick all that apply)

- I forgot to take my study medication

Ticking the above will prompt the following option, if ticked, the trial team will action:

- Would you like a daily reminder sent to you via email/push notification

- I was prescribed another medication and my doctor told me to stop taking my study medication

Ticking the above will prompt an alert for the trial team to contact surgery for details and consider withdrawal from study

- My doctor recommended that I stop taking study medication because of muscle symptoms

Ticking the above will prompt an alert for the trial team to contact surgery for details

- I decided to stop taking study medication because of muscle symptoms

Ticking the above will prompt an alert for the patient to contact the GP for advice

- I didn't want to take my study medication

Ticking the above will prompt the following option, if ticked NO, the trial team will arrange for end of trial:

Do you still wish to participate in the trial: Yes No

- Other (please specify)

(free text)

PART 2: EXPLORING SYMPTOMS IN THE PAST TWO MONTHS

1. *(all participants):* In the last two months, have you experienced muscle symptoms, e.g. muscle pain or weakness?

Yes
 No

2. *(appears if the participant ticks yes for Question 1):* Do you think these muscle symptoms are related to your study medication?

Yes
 No
 Don't know

[figure not shown]
3. *(appears if the participant ticks no for Question 2):* What do you think may have caused these muscle symptoms?
(free text)

Don't know

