[figure not shown]
4. *(appears if the participant ticks yes for Question 1):* Indicate with a cross (x) on the scale the number that describes how, during the last two months, pain has interfered with your:

- General activity
- Mood
- Walking ability
- Normal work (includes both work outside the home and housework)
- Relations with other people
- Sleep
- Enjoyment of life

For each of (a) to (g), the following scale will appear:

5. (appears if the participant ticks yes for Question 1): **On the diagram, tap to highlight the area that hurts the most.**
(Paper form will read: 'On the diagram, put an X on the area that hurts the most.')

More than one area

The body will be divided into the following locations and answers should be categorized depending where the participant taps. For paper forms, the location given by X marked on the body will be entered into the web or app version at data entry. Locations: head and neck/upper limbs/lower limbs/trunk.

6. (All participants): **In the last two months, have you experienced any other symptom that you think is associated with your study medication?**

Yes (please specify)
(free text)
 No
 Don't know

PART 3: ADVERSE EVENTS

1. (All participants): **Have you been admitted to hospital in the last two months?**

Yes
 No

[figure not shown]
[figure not shown]
2. (Appears if the participant ticks yes for Question 1): **What was the reason for your admission to hospital?**

[figure not shown]
[figure not shown]
[figure not shown]
[figure not shown]
(free text)

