Appendix 5: StatinWISE VAS Pain Scale data form

You will be asked to complete this form each day during the last seven days of each two-month treatment period.

Day	Daily symptoms report		
1	1. Did you take study medication yesterday? No  Yes 	2. Did you experience muscle symptoms today? No  Yes  If yes:	3: Please indicate severity of muscle symptoms you experienced today.  0 No symptoms 5 Moderate symptoms 10 Worst possible symptoms
2	1. Did you take study medication yesterday? No  Yes 	2. Did you experience muscle symptoms today? No  Yes  If yes:	3: Please indicate severity of muscle symptoms you experienced today.  0 No symptoms 5 Moderate symptoms 10 Worst possible symptoms
3	1. Did you take study medication yesterday? No  Yes 	2. Did you experience muscle symptoms today? No  Yes  If yes:	3: Please indicate severity of muscle symptoms you experienced today.  0 No symptoms 5 Moderate symptoms 10 Worst possible symptoms

4	
1. Did you take study medication yesterday? No  Yes 
 
2. Did you experience muscle symptoms today? No  Yes  If yes:
 
3: Please indicate severity of muscle symptoms you experienced today.
 
5	
1. Did you take study medication yesterday? No  Yes 
 
2. Did you experience muscle symptoms today? No  Yes  If yes:
 
3: Please indicate severity of muscle symptoms you experienced today.
 
6	
1. Did you take study medication yesterday? No  Yes 
 
2. Did you experience muscle symptoms today? No  Yes  If yes:
 
3: Please indicate severity of muscle symptoms you experienced today.
 
7	
1. Did you take study medication yesterday? No  Yes 
 
If yes:
 
2. Did you experience muscle symptoms today? No  Yes  If yes:
 
3: Please indicate severity of muscle symptoms you experienced today.
 

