5.2 PHARMACOKINETIC PROPERTIES

Absorption

Atorvastatin is rapidly absorbed after oral administration; maximum plasma concentrations (C_{max}) occur within 1 to 2 hours. Extent of absorption increases in proportion to atorvastatin dose. After oral administration, atorvastatin film-coated tablets are 95% to 99% bioavailable compared to the oral solution. The absolute bioavailability of atorvastatin is approximately 12% and the systemic availability of HMG-CoA reductase inhibitory activity is approximately 30%. The low systemic availability is attributed to presystemic clearance in gastrointestinal mucosa and/or hepatic first-pass metabolism

Distribution

Mean volume of distribution of atorvastatin is approximately 381 L. Atorvastatin is $\geq 98\%$ bound to plasma proteins.

Metabolism

Atorvastatin is metabolised by cytochrome P450 3A4 to ortho- and parahydroxylated derivatives and various beta-oxidation products. Apart from other pathways these products are further metabolised via glucuronidation. *In vitro*, inhibition of HMGCoA reductase by ortho- and parahydroxylated metabolites is equivalent to that of atorvastatin. Approximately 70% of circulating inhibitory activity for HMG-CoA reductase is attributed to active metabolites.

Excretion

Atorvastatin is eliminated primarily in bile following hepatic and/or extrahepatic metabolism. However, atorvastatin does not appear to undergo significant enterohepatic recirculation. Mean plasma elimination half-life of atorvastatin in humans is approximately 14 hours. The half-life of inhibitory activity for HMG-CoA reductase is approximately 20 to 30 hours due to the contribution of active metabolites.

Special populations

- Elderly: Plasma concentrations of atorvastatin and its active metabolites are higher in healthy elderly subjects than in young adults while the lipid effects were comparable to those seen in younger patient populations.

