1.7 DEFINITION OF PRIMARY OUTCOME

The primary outcome is patient reported muscle symptoms (pain, weakness, tenderness, stiffness or cramp to the body), on a Visual Analogue Scale (VAS), with possibly responses ranging from 0 to 10. This will be collected daily via the VAS Pain Scale data form (Appendix 1) during the last 7 days of each of the 6 treatment periods via the patient's nominated collection method (app, website, phone call, or paper form).

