2.3.2 SECONDARY OUTCOMES

Descriptive analyses of muscle symptoms

Details of symptoms experienced (whether the patient believes they were caused by the study medication, the site, the extent to which the pain impacts on other aspect of life, other symptoms experienced) will be reported for all periods in which the patient reports experiencing muscle symptoms. For these descriptions, the denominator will be the number of periods in which symptoms are experienced; no attempt will be made to account for the clustering by patient. These descriptive statistics will be repeated splitting by treatment actually received.

Descriptions of symptoms experienced will also be made using the patient as the unit of analysis. For these descriptions, patient-level variables for patients who report one or more period where they experienced muscle symptoms will be defined as follows: (i) a new location variable: always multiple sites/sometimes multiple sometimes single/always single site, (ii) four new site variables indicating symptoms ever experienced in head/neck versus not, etc., and (iii) mean VAS score for impacts on other aspects of life across periods in which symptoms were experienced by that patient.

Because these descriptive statistics do not respect the randomised allocation of treatment, no comparisons between treatment groups will be made; no formal statistical inference will be undertaken.

Randomised comparisons of muscle symptoms experienced

The patient questionnaire collects a binary measure of whether the patient experienced muscle symptom or not during that treatment period. This binary measure will be compared between randomized treatment groups (statin – placebo) with an odds ratio and confidence interval, obtained using a logistic mixed model with random participant and random treatment effects with an unstructured covariance matrix between random effects.

As a more specific measure, a single binary outcome of whether the participant reports having muscle symptoms that they believe to be caused by the study medication will be derived (taking the values one if the participant reports symptoms and that they believe these are – or they don't know whether they are – related to the study medication, and zero if either the participant has no symptoms or the participant has symptoms but does not believe these are related to the study medication). This binary measure will be analysed as described in the previous paragraph.

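### SAP 2.3.4 rules out any carry-over check on grounds that hold for the week-8 daily VAS but not for the two-month questionnaire outcomes, where run-on symptoms would pull the statin-placebo contrast toward no difference

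*SAP*

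**What the plan says.** Under its heading on period and carry-over effects, SAP 2.3.4 adds fixed period effects to the primary and secondary outcome models as a sensitivity analysis. It then states: "We will not explore carry-over effects; the trial was designed to avoid such effects". It makes no exception by outcome and does not name the design feature it relies on.

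That feature is not a washout. Protocol 2.9.3 says: "Ideally there should be no break between treatment periods".

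The outcomes have different recall windows:

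- **Daily VAS (primary).** SAP 1.7 collects it "during the last 7 days of each of the 6 treatment periods", and the form in Protocol Appendix 5 asks: "Please indicate severity of muscle symptoms you experienced today".
- **Questionnaire (secondary), completed once per period on day 56.** Protocol Appendix 4, Part 2, asks: "In the last two months, have you experienced muscle symptoms, e.g. muscle pain or weakness". The attribution item refers to those same symptoms. The seven impact items ask how, "during the last two months, pain has interfered with your", various activities.

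SAP 2.3.2 uses the questionnaire answers for randomised comparisons: "The patient questionnaire collects a binary measure of whether the patient experienced muscle symptom or not during that treatment period". The any-symptom and attributed-symptom outcomes go into logistic mixed models, and the seven impact scores into linear mixed models. A don't-know answer on attribution counts as attributed. Impact scores are set to zero only in periods with no reported symptoms.

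**The concern.** The two-month window opens on the day the patient changes capsule. A patient whose statin-period soreness lasts a day or more into the next period can truthfully answer yes for that period, even if it is placebo and nothing new happened in it. One yes marks the whole period as symptomatic, and it also replaces a zero with a recorded impact score. The reason given for not looking at carry-over therefore does not apply to these outcomes.

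The direction matters. Alternation within pairs means placebo periods follow statin far more often than statin periods do, so run-on reporting makes the two treatments look more alike. In a trial meant to separate statin effects from nocebo effects, false similarity on the symptom and attribution outcomes is the error most likely to be misread. Fixed period effects, the only related check planned, do not model the previous treatment.

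**Working it through.** The plan gives no figure for carry-over, so there is none to reproduce. The checks below use the plan's own design.

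**1. Exposure to the previous treatment** (eight equally likely sequences, Protocol 2.8; 24 placebo and 24 statin periods):

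| Current period | After statin | After placebo | Period 1 |
|---|---|---|---|
| Placebo | 16 (67%) | 4 | 4 |
| Statin | 4 (17%) | 16 | 4 |

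**2. Residual drug.** The product characteristics in Protocol Appendix 8, section 5.2, say: "The half-life of inhibitory activity for HMG-CoA reductase is approximately 20 to 30 hours". Five half-lives are 5 × 20 to 30 h = 100 to 150 h, or 4.2 to 6.3 days. At 30 h, activity left after 7 days is 0.5^(168/30) = 2%; after 49 days it is effectively nil. The week-8 VAS is therefore clear of residual drug. The questionnaire window includes those first days, and also any later days on which symptoms are still resolving.

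**3. Impact scores.** Let L be the fraction of the statin effect that is also reported in the next period (assumed; not in the documents). If carry-over is additive in every period after statin, the estimated difference is the true one times 1 + L(4/24 − 16/24) = 1 − 0.5L. That is 95% of the true difference at L = 0.1, 87.5% at 0.25 and 75% at 0.5.

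**4. Any-symptom outcome.** Assumed rates are p0 = 30% on placebo and p1 = 45% on statin, so the true odds ratio is (0.45/0.55)/(0.30/0.70) = 1.91. The statin-caused risk is e = 1 − 0.55/0.70 = 0.214. If a fraction c of statin-caused episodes is reported in the next period, whatever its treatment:

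- placebo rate q0 = 1 − 0.70 × (1 − (16/24)·c·e)
- statin rate q1 = 1 − 0.55 × (1 − (4/24)·c·e)

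| c | q0 | q1 | Odds ratio |
|---|---|---|---|
| 0 | 30.0% | 45.0% | 1.91 |
| 5% | 30.5% | 45.1% | 1.87 |
| 10% | 31.0% | 45.2% | 1.84 |
| 25% | 32.5% | 45.5% | 1.73 |
| 50% | 35.0% | 46.0% | 1.58 |
| 100% | 40.0% | 47.0% | 1.33 |

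These are population-averaged odds ratios. The SAP's mixed model estimates participant-specific ones, so the table shows direction and rough scale only.

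**5. Can it be checked, and at what cost?** Yes. Statin-after-statin and placebo-after-placebo transitions occur, so a previous-treatment term can be estimated. In a linear model with participant effects, all six periods kept and Period 1 coded as no previous trial treatment, the treatment variance for one set of eight sequences (residual variance 1) is:

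- without the term: 0.0833
- with the term: 0.1133, SE ratio √(0.1133/0.0833) = 1.17
- with the term and fixed period effects: 0.1208, SE ratio √(0.1208/0.0833) = 1.20

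For scale, take 120 completers (200 × 0.6, from the 40% loss in Protocol 2.4) and a period-level SD of 30, the within-participant VAS figure in Protocol 2.3 applied by assumption to the impact scores. The treatment SE goes from 2.24 to 2.69 with period effects, and the SE of the previous-treatment term is 3.0.

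**The case against.** The best defence is that the trial's answer rests on the week-8 daily VAS. The SAP ranks the questionnaire outcomes below it, reports them with 99% intervals and already has a week-8 measure of symptoms in the primary analysis. Drug activity covers only about 4 to 6 of 56 days, no document says how long symptoms last after stopping, and at 5-10% run-on the odds ratio barely moves. Relying on design rather than a first-order carry-over term is a respectable choice.

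Much of this stands. It limits the point to secondary outcomes and leaves the size open. It does not rescue the SAP's sentence, which covers outcomes that lack the design protection it cites.

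Two stronger readings are tempting, and the documents do not support them:

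- **That patients still on a statin at entry bias Period 1 in the same way.** Half the sequences start on each treatment, so pre-trial statin use is independent of Period 1 allocation. An additive carry-in acts as a period effect, which SAP 2.3.4 already allows for in sensitivity models. Only some non-additive dilution could remain.
- **That a week-8 version of the attributed-symptom outcome would cure the problem.** The daily form has no attribution question. The only attribution answer comes from the two-month questionnaire, so the recall window would return with it.

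**Conclusion.** The point holds for the questionnaire outcomes in SAP 2.3.2: any muscle symptoms, attributed symptoms and the seven impact scores. For these, no carry-over is an untested assumption rather than a property of the design, and the bias, if present, is toward no difference.

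A reader might infer that the trial's main conclusion is at risk. The documents do not support that: the primary VAS asks about the same day, about seven weeks after the switch, and would be affected only by symptoms lasting longer than that.

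The transition counts and recall windows are certain. The size is not. The odds ratios of 1.87 to 1.33 rest on assumed symptom rates and assumed run-on fractions. The point justifies a change to the SAP, at the level of a worthwhile and inexpensive improvement.

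**What to change.** 1. In SAP 2.3.4, limit the statement that the design avoids carry-over to the week-8 daily VAS, and acknowledge possible dilution for the two-month items.
2. Add to SAP 2.3.4, for the questionnaire outcomes, a sensitivity model with previous-period treatment as a covariate, Period 1 coded as no previous trial treatment, and fixed period effects. Note that the treatment SE rises about 17-20%, which is why this should not replace the main model.
3. Beside the two-month any-symptom outcome, report a week-8 version: at least one yes on the daily symptom question in the last seven days of the period, analysed by the same logistic mixed model. State that it misses symptoms that resolved before week 8, so it complements the two-month outcome and does not answer an identical question. Do not add a week-8 attributed version.

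The cost is SAP wording and a few extra models on data already collected. SAP section 1 allows changes until the plan is finalised before database lock.

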2.3.5 SUBGROUP ANALYSES

There are no a priori subgroup analyses planned. If an overall population-level effect is detected, we may investigate whether the effect varies within subgroups defined by measured baseline characteristics. These analyses will be regarded and interpreted as being exploratory.

2.3.6 ADJUSTED ANALYSES

Comparisons are made within the same participant, comparing placebo with statin periods. Thus, baseline imbalance of patient characteristics will not occur. No adjusted analyses will be performed.

2.3.7 SECONDARY ANALYSES

Withdrawal, Loss to follow-up and Adherence – Descriptive analyses

Loss to follow up and withdrawal, with reasons for withdrawal, will be summarized by overall frequencies and percentages. Protocol violations will be tabulated. Descriptive statistics, including graphical summaries, will be used to summarise the measures of adherence to randomized treatment and withdrawal, and their relationship to the statin and placebo periods.

Withdrawal – Comparison between statin and placebo periods

We will explore whether the period in which a patient was first known to have withdrawn was more likely to have been a placebo or a statin period. If this date is after the end of a treatment period but the patient chooses not to begin the next period, the period in which the withdrawal happens will be set to the period just ended.

Adherence – Randomised comparison

We will explore whether adherence was lower on statin periods compared with placebo periods using mixed models similar to those described above.

Adherence – Efficacy analyses

We will use the measures of adherence to randomised treatment to perform an efficacy analysis based around an instrumental variables approach. Because these analyses require much stronger assumptions than the intention-to-treat analysis above, the results of the efficacy analysis will be presented and interpreted as a secondary analysis.

